10.13. Appendix 13: Immune Related Response Criteria Derived from RECIST 1.1 (irRECIST)

Increasing clinical experience indicates that traditional response criteria may not be sufficient to fully characterize activity in this new era of targeted therapies and/or biologics.

The irRECIST tumor assessment system has been developed to incorporate delayed or flare type- responses into the RECIST v1.1 ([Nishino et al, 2014](#)).

For irRECIST, only target and measurable lesions are taken into account. In contrast to RECIST v1.1, irRECIST:

- Requires confirmation of both progression and response by imaging at least 4 weeks from the date first documented, and
- Does not necessarily score the appearance of new lesions as progressive disease if the sum of lesion diameters of target lesions (minimum of 10 mm longest diameter per non-nodal lesion and 15 mm shortest diameter per nodal lesion, maximum of 5 target lesions, maximum of 2 per organ) and measurable new lesions does not increase by ≥20%.

The same method of assessment and the same technique should be used to characterize each identified and reported target lesion(s) at baseline and throughout the trial.

irRECIST is defined as follows:

- Overall immune-related complete response (irCR): Complete disappearance of all lesions (whether measurable or not) and no new lesions. All measurable lymph nodes also must have a reduction in short axis to <10 mm.
- Overall immune-related partial response (irPR): Sum of the diameters (longest for non-nodal lesions, shortest for nodal lesions) of target and new measurable lesions decreases ≥30%.
- Overall immune-related stable disease (irSD): Sum of the diameters (longest for non-nodal lesions, shortest for nodal lesions) of target and new measurable lesions is neither irCR, irPR, (compared to baseline) or immune-related progressive disease (irPD, compared to nadir).
- Overall immune-related progressive disease (irPD): Sum of the diameters (longest for non-nodal lesions, shortest for nodal lesions) of target and new measurable lesions increases ≥20% (compared to nadir), confirmed by a repeat, consecutive observation at least 4 weeks from the date first documented.

New measurable lesions: Incorporated into tumor burden (ie, added to the target lesion measurements). A lymph node has to be ≥15 mm in short axis to be a measurable new lesion

and its short axis measurement is included in the sum. Up to 2 new lesions per organ and up to 5 new lesions in total can be added to the measurements.

New non-measurable lesions: Do not define progression but preclude irCR.

Overall responses derived from changes in index, nonindex, and new lesions are outlined in Table 20.

[figure not shown]
Table 20. Overall Response Derived from Changes in Index, Non-index and New Lesions

Measurable Response	Nonmeasurable- Response		Overall Response Using irRECIST ^b
Index and New Measurable Lesions (Tumor Burden) ^a	NonIndex- Lesions	Measurable Lesions	
Decrease 100%	Absent	Absent	irCR
Decrease 100%	Stable	Any	irPR
Decrease 100%	Unequivocal progression	Any	irPR
Decrease $\geq 30\%$	Absent/stable	Any	irPR
Decrease $\geq 30\%$	Unequivocal progression	Any	irPR
Decrease $< 30\%$ and increase $< 20\%$	Absent/stable	Any	irSD
Decrease $< 30\%$ and increase $< 20\%$	Unequivocal progression	Any	irSD
Increase $\geq 20\%$	Any	Any	irPD

a. Decrease assessed relative to baseline.

b. Response (irCR and irPR) and progression (irPD) must be confirmed by a second, consecutive assessment at least 4 weeks apart.

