All sites of disease must be assessed at baseline. Baseline assessments should be done as close as possible prior to study start. For an adequate baseline assessment, all required scans must be done within 28 days prior to treatment and all disease must be documented appropriately. If baseline assessment is inadequate, subsequent statuses generally should be indeterminate.

Note: For the participant population being evaluated in this protocol, the baseline assessment may be completed within 6 weeks prior to randomization.

Target Lesions

All measurable lesions up to a maximum of 2 lesions per organ, 5 lesions in total, representative of all involved organs, should be identified as target lesions at baseline. Target lesions should be selected on the basis of size (longest lesions) and suitability for accurate repeated measurements. Record the longest diameter for each lesion, except in the case of pathological lymph nodes for which the short axis should be recorded. The sum of the diameters (longest for non-nodal lesions, short axis for nodal lesions) for all target lesions at baseline will be the basis for comparison to assessments performed on study.

If 2 target lesions coalesce the measurement of the coalesced mass is used. If a large target lesion splits, the sum of the parts is used.

Measurements for target lesions that become small should continue to be recorded. If a target lesion becomes too small to measure, 0 mm should be recorded if the lesion is considered to have disappeared; otherwise a default value of 5 mm should be recorded.

NOTE: When nodal lesions decrease to <10 mm (normal), the actual measurement should still be recorded.

Non-target Disease

All non-measurable disease is non-target. All measurable lesions not identified as target lesions are also included as non-target disease. Measurements are not required but rather assessments will be expressed as ABSENT, INDETERMINATE, PRESENT/NOT INCREASED, INCREASED. Multiple non-target lesions in 1 organ may be recorded as a single item on the case report form (eg, 'multiple enlarged pelvic lymph nodes' or 'multiple liver metastases').

Objective Response Status at Each Evaluation

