Disease sites must be assessed using the same technique as baseline, including consistent administration of contrast and timing of scanning. If a change needs to be made the case must be discussed with the radiologist to determine if substitution is possible. If not, subsequent objective statuses are indeterminate.

Target Disease

Complete Response (CR): Complete disappearance of all target lesions with the exception of nodal disease. All target nodes must decrease to normal size (short axis <10 mm). All target lesions must be assessed.

Partial Response (PR): Greater than or equal to 30% decrease under baseline of the sum of diameters of all target measurable lesions. The short diameter is used in the sum for target nodes, while the longest diameter is used in the sum for all other target lesions. All target lesions must be assessed.

Stable: Does not qualify for CR, PR, or Progression. All target lesions must be assessed. Stable can follow PR only in the rare case that the sum increases by less than 20% from the nadir, but enough that a previously documented 30% decrease no longer holds.

Objective Progression (PD): 20% increase in the sum of diameters of target measurable lesions above the smallest sum observed (over baseline if no decrease in the sum is observed during therapy), with a minimum absolute increase of 5 mm.

Indeterminate: Progression has not been documented, and

- one or more target measurable lesions have not been assessed;
- or assessment methods used were inconsistent with those used at baseline;
- or 1 or more target lesions cannot be measured accurately (eg, poorly visible unless due to being too small to measure);
- or 1 or more target lesions were excised or irradiated and have not reappeared or increased.

Non-target Disease

CR: Disappearance of all non-target lesions and normalization of tumor marker levels. All lymph nodes must be 'normal' in size (<10 mm short axis).

Non-CR/Non-PD: Persistence of any non-target lesions and/or tumor marker level above the normal limits.

PD: Unequivocal progression of pre-existing lesions. Generally, the overall tumor burden must increase sufficiently to merit discontinuation of therapy. In the presence of SD or PR in target disease, progression due to unequivocal increase in non-target disease should be rare.

Indeterminate: Progression has not been determined and 1 or more non-target sites were not assessed or assessment methods were inconsistent with those used at baseline.

New Lesions

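### irRECIST progression has no written 5 mm minimum, so its size trigger is looser than RECIST 1.1 when the nadir sum is below 25 mm; and the irCR text and Table 20 disagree on nodes that have shrunk below 10 mm

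*Protocol*

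**What the plan says.** **Progression.** Appendix 13 (Protocol Section 10.13) calls irPD when the sum of diameters "of target and new measurable lesions increases ≥20% (compared to nadir), confirmed by a repeat, consecutive observation at least 4 weeks" after first documentation. Table 20 repeats the 20% figure. Neither gives an absolute minimum. Appendix 12 (Section 10.12) also uses 20% over the smallest sum for RECIST 1.1, but "with a minimum absolute increase of 5 mm".

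Appendix 13 is headed as derived from RECIST 1.1. After the words "In contrast to RECIST v1.1, irRECIST" it lists two differences: confirmation of both response and progression, and the handling of new lesions. Dropping the 5 mm minimum is not listed.

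**Complete response.** The irCR definition in Appendix 13 says: "All measurable lymph nodes also must have a reduction in short axis to <10 mm". This matches the nodal rule in Appendix 12: "All target nodes must decrease to normal size (short axis <10 mm"). Table 20 gives irCR only in the row for a 100% decrease, and its footnote says: "Decrease assessed relative to baseline". Neither the rows nor the footnotes make an exception for nodes. On recording, Appendix 12 says: "When nodal lesions decrease to <10 mm (normal), the actual measurement should still be recorded".

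**Use.** ORR, DOR, PFS and TTP by irRECIST are Part 2 secondary endpoints (Protocol Section 3). SAP Section 5.2.1 lists irCR, irPR and irPD as separate binary endpoints. SAP Section 6.2.4 says irRECIST response is handled in a similar way to RECIST response and gives no irPD or irCR rule of its own. Protocol Section 4.1 and SAP Section 2.2 also continue treatment until irRECIST progression.

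**The concern.** Appendix 13 exists to accommodate delayed and flare responses, so one expects its progression rule to be at least as tolerant as RECIST 1.1. For growth in a small residual sum it is less tolerant. A change within ordinary measurement error can meet the threshold, and a second reading can confirm it. The people affected are those with the deepest responses, whose irRECIST PFS, TTP and DOR could be given an event date that is too early.

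The complete-response problem is different. The text and the table give different answers for the same participant, and nothing says which prevails. Two programmers working correctly from Appendix 13 could report different irCR and irPR rates. With about 20 participants per cohort, one reclassified responder moves a rate by 1/20 = 5 percentage points.

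**Working it through.** The plan gives no figure to reproduce, so the check takes the written thresholds and asks what they imply.

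**1. Smallest increase that meets each rule.** With nadir sum N in mm, irPD needs 0.20 × N, and RECIST 1.1 PD needs the larger of 0.20 × N and 5. The two agree once 0.20 × N ≥ 5, that is N ≥ 5/0.20 = 25 mm.

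| Nadir sum (mm) | irPD: increase (new sum) | RECIST 1.1 PD: increase (new sum) |
|---|---|---|
| 5 | 1.0 (6.0) | 5.0 (10.0) |
| 8 | 1.6 (9.6) | 5.0 (13.0) |
| 9 | 1.8 (10.8) | 5.0 (14.0) |
| 18 (two 9 mm nodes) | 3.6 (21.6) | 5.0 (23.0) |
| 25 | 5.0 (30.0) | 5.0 (30.0) |
| 27 (three 9 mm nodes) | 5.4 (32.4) | 5.4 (32.4) |

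Suppose the only remaining target lesion is a node that goes from 8.0 to 9.6 mm. It meets the irPD threshold, subject to confirmation, while still below 10 mm, and its RECIST 1.1 target status is still CR. At N = 0 a percentage increase is undefined; written as a multiple (1.2 × 0 = 0), any measurement satisfies it.

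**2. Does confirmation remove the problem?** The documents give no measurement error, so this step rests on assumptions:
- the true residual sum is constant, and the baseline sum is twice that value;
- each reading has independent normal error with SD 1 mm (range 0.5 to 2 mm);
- the nadir is the smallest sum observed so far;
- irPD is confirmed if the next scan is also at or above the threshold set by the same nadir.

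Scans at weeks 8, 16 and 24 and then every 12 weeks (Protocol Section 8.1.1) put the third scan at week 24 and the sixth at week 24 + 3 × 12 = 60. Simulation with at least 200,000 participants per setting gives the chance of at least one false confirmed irPD:

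| True sum | Six scans, as written | Six scans, with 5 mm minimum |
|---|---|---|
| 8 mm | 34% (3 to 65%) | <0.1% (at most 6%) |
| 12 mm | about 12% (0.1 to 49%) | <0.1% (at most 6%) |
| 16 mm | 3% (0 to 34%) | <0.1% (at most 6%) |

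The main figure is for SD 1 mm; brackets show SD 0.5 and 2 mm. The last column is the same in every row because the 5 mm condition governs whenever the nadir is below 25 mm. With only three scans, the 8 mm case as written gives about 7% (0.5 to 17%).

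**3. Complete response.** A target node must start at "15 mm shortest diameter per nodal lesion" or more. A lone node that falls from 15 to 9 mm has decreased by 1 − 9/15 = 40%. It is irCR by the text, because it is under 10 mm, and irPR by Table 20, because the decrease is at least 30% but not 100%. A node going 15, 6, 8 mm shows the conflict more sharply. At 8 mm it is 1 − 8/15 = 46.7% below baseline (irPR by the table), under 10 mm (irCR by the text), and (8 − 6)/6 = 33.3% above nadir, which meets the irPD threshold pending confirmation. No order of precedence is given.

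**The case against.** The best defence is that Appendix 13 inherits whatever it does not change. It is derived from RECIST 1.1, the missing minimum is not among its stated differences, and the SAP handles irRECIST response similarly to RECIST. On that reading the 5 mm minimum already applies. The reading is tenable, but the irPD definition and Table 20 are written as complete rules, and a programmer following them would apply 20% alone. The omission could equally be deliberate, following the cited irRECIST source; the documents do not say.

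Several limits stand:
- The 1 to 2 mm trigger needs the whole nadir sum, target plus new measurable lesions, to be 10 mm or less. A small node alongside larger disease is not exposed.
- The 34% figure is conditional on an 8 mm sum followed for about 60 weeks.
- The study tests no hypotheses, and RECIST 1.1 results are reported alongside.

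A reader might also infer more than the documents support:
- *irRECIST calls progression earlier than RECIST 1.1 in general.* It does not. RECIST 1.1 progresses on any unequivocal new lesion or unequivocal non-target progression, without confirmation, and Appendix 13 does not. The looser trigger concerns only growth in a small sum.
- *Nodal complete responders are scored irPR, so irCR is undercounted.* That assumes the table overrides the text, and nothing says so.
- *A participant with a target node can never reach a 100% decrease.* Appendix 12 records 0 mm for a target lesion that is too small to measure and considered gone. Only a node with a recorded residual size is blocked.
- *The irRECIST ORR is affected by the irCR conflict.* If ORR counts irCR plus irPR, moving a responder between them leaves it unchanged.

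**Conclusion.** The point holds in two limited parts.

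First, as written, irPD has a looser size trigger than RECIST 1.1 whenever the nadir sum is below 25 mm, and it is not defined at a nadir of zero. Confirmation reduces false calls but does not remove them. Their frequency depends on the assumed SD, independent errors and the number of scans. The effect on the cohort-level PFS, TTP and DOR summaries cannot be sized, because the documents give no basis for the number of participants with such small sums.

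Second, Appendix 13 contradicts itself on irCR for a residual target node under 10 mm. This changes the separate irCR and irPR rates in SAP Section 5.2.1.

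Both are drafting faults in a definition that feeds named endpoints. They are worth correcting before the irRECIST derivations are programmed, but they do not touch the primary safety endpoints.

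**What to change.** - **SAP Section 6.2.4:** for deriving irRECIST PFS, TTP, DOR and the irPD rate, state that irPD needs an increase over nadir of at least 20% and at least 5 mm, as in Appendix 12. State how a nadir of zero is handled.
- **Table 20, irCR row:** replace the 100% decrease with the condition in the text, so that all non-nodal lesions are absent and all nodes are under 10 mm in short axis.
- **Treatment passages:** Protocol Section 4.1 and SAP Section 2.2 use irRECIST progression to end treatment. The sponsor must reconcile them with Appendices 12 and 13. Which criterion should govern treatment is a clinical decision, and none is proposed here.

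The cost is wording in one appendix table and one SAP section, plus the sponsor's reconciliation. It needs no new scans or data, because the lesion measurements are already collected.

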10.14. Appendix 14: Subcutaneous Injection Site Locations

Injection site locations include a maximum of 8 unique administration sites distributed across 4 abdominal quadrants with a possibility of up to 2 injection locations per quadrant. Location 1 is proximal to the umbilicus and Location 2 is distal to the umbilicus.

Administer the required number of injections in the following order:

1. Lower Left Quadrant Location 1;
2. Lower Right Quadrant Location 1;
3. Lower Left Quadrant Location 2;
4. Lower Right Quadrant Location 2;
5. Upper Right Quadrant Location 1;
6. Upper Left Quadrant Location 1;
7. Upper Right Quadrant Location 2;
8. Upper Left Quadrant Location 2.

Injections to the abdomen are preferred. If SC injections in the abdominal location are not possible, SC injections can be administered in a distributed manner in the thighs. SC injections in the upper extremities (eg, deltoid, upper and lower arm) are not permitted.

Track the participant's injection site(s) sequentially on this diagram with a red pen and mark the injection sites on the patient's abdomen according to your clinic's standard practice.

Record the location, time of each injection and any ISRs in the participant's source records and study CRF. Complete 1 CRF per injection.

10.15. Appendix 15. Cautionary Use of Concomitant Medications with Narrow Therapeutic Index Due to Drug-Drug Interaction (DDI) Potential.

Medications listed below have narrow therapeutic index and should be used with caution as concomitant treatment with PF-07260437. It has been known that CRS is mostly likely to occur within the first few days after the first dose, and the increased cytokine level could potentially down-regulate CYP450 enzymes and alter the exposure of drugs that are substrates of these enzymes. The Pfizer study team should be notified of any listed medications taken during the study for consultation.

This list of drugs for potential DDI concerns with the PF-07260437 may be revised during the course of the study with written notification from sponsor, to include or exclude specific drugs or drug categories for various reasons (eg, emerging DDI results for PF-07260437, new information in literatures on the DDI potential of other drugs).

This is not an all-inclusive list. Shared substrates for multiple CYP450 enzymes are listed one time to avoid duplication. Site staff should consult with the sponsor or designee with any questions regarding potential DDI.

Drug Category	Drugs
CYP3A4 Substrate	alfentanil amiodarone argatroban carbamazepine cyclosporine dihydroergotamine ergotamine everolimus fentanyl pimozide quinidine rifampin sirolimus tacrolimus valproate
CYP2C9 Substrate	acenocoumarol isotretinoin phenytoin Phenobarbital phenprocoumon warfarin
CYP2C19 Substrate	mephenytoin
CYP1A2 Substrate	theophylline tizanidine
CYP2B6 Substrate	carbamazepine

Drug Category	Drugs
	cyclophosphamide

Investigators should consult the product label for any other medication used during the study for information regarding medication that is prohibited for concomitant use.

10.16. Appendix 16: ECOG Performance Status

Grade	ECOG Performance Status
0	Fully active, able to carry on all pre-disease performance without restriction.
1	Restricted in physically strenuous activity but ambulatory and able to carry out work of a light or sedentary nature, eg, light housework, office work.
2	Ambulatory and capable of all self-care but unable to carry out any work activities. Up and about more than 50% of waking hours.
3	Capable of only limited self-care, confined to bed or chair more than 50% of waking hours.
4	Completely disabled. Cannot carry on any self-care. Totally confined to bed or chair.
5	Dead.

10.17. Appendix 17: Abbreviations

The following is a list of abbreviations that may be used in the protocol

Abbreviation	Term
2L+	after first line standard of care
ACTH	adrenocorticotropic hormone
ADA	antidrug antibodies
ADL	activities of daily living
AE	adverse event
AHA	American Heart Association
AIDS	acquired immunodeficiency syndrome
ALP	alkaline phosphatase
ALT	alanine aminotransferase
ANC	absolute neutrophil count
aPTT	activated partial thromboplastin time
ASCO	American Society of Clinical Oncology
AST	aspartate aminotransferase
ASTCT	American Society for Transplantation and Cellular Therapy
AT	aminotransferases
AUC	area under the curve
AUC _{inf}	area under the concentration-time versus time curve from time 0 to infinity
AUC _{last}	area under the concentration-time curve from time 0 to time of last measurable concentration
AUC _{sd,τ}	area under the concentration-time curve after single dose over dosing interval τ
AUC _{ss,τ}	area under the concentration-time curve at steady state over dosing interval τ
AV	atrioventricular
B	B cells
BBS	Biospecimen Banking System
BiPAP	bilevel positive airway pressure
BLRM	Bayesian logistic regression model
BNP	brain natriuretic peptide
BP	blood pressure
Bpm	beats per minute
BrCa	breast cancer
BUN	blood urea nitrogen
BVN	bivariate normal
C	cycle
CAR	chimeric antibody receptor
CD3	Cluster-Defined 3
CDC	The Centers for Disease Control and Prevention

Abbreviation	Term
CDK	cyclin-dependent kinase
CFR	Code of Federal Regulations
CHF	congestive heart failure
CI	confidence interval
CIOMS	Council for International Organizations of Medical Sciences
CISH	chromogenic in situ hybridization
CK	creatine kinase
CK-MB	creatine kinase-muscle type, myocardial band
CL	clearance
CL/F	apparent clearance
CL _{ss} /F	apparent clearance at steady state
CLIA	Clinical Laboratory Improvement Amendments
C _{max}	maximum observed concentration
C _{max,ss}	maximum concentration at steady state
C _{min,ss}	minimum concentration at steady state
CNS	central nervous system
CO ₂	carbon dioxide
CONSORT	Consolidated Standards of Reporting Trials
COVID-19	coronavirus disease 2019
CPAP	continuous positive airway pressure
CR	complete response
CrCl	creatinine clearance
CRF	case report form
CRO	contract research organization
CRP	c-reactive protein
CRS	cytokine release syndrome
CSF	cerebral spinal fluid
CSR	clinical study report
CT	clinical trial/ computed tomography
CTCAE	Common Terminology Criteria for Adverse Events
CTLs	Cytotoxic T lymphocytes
CYP	cytochrome P-450 enzymes;
D	day
DDI	drug-drug interaction
DILI	drug-induced liver injury
DISH	dual in situ hybridization
DLT	dose-limiting toxicity
DMC	data monitoring committee
DNA	deoxyribonucleic acid
DoR	duration of response
DRE	disease related events
DU	dispensable unit

Abbreviation	Term
EC	ethics committee
EC ₅₀	half maximal effective concentration
ECC	emergency contact card
ECG	electrocardiogram
ECHO	echocardiogram
ECOG	Eastern Cooperative Oncology Group
eCRF	electronic case report form
EDB	exposure during breastfeeding
EDP	exposure during pregnancy
EEG	electroencephalogram
EMA	European Medicines Agency
EOT	end of treatment
ER	estrogen receptor
ESC	European Society of Cardiology
EU	European Union
EudraCT	European Clinical Trials Database
EWOC	escalation with overdose control
FAS	full analysis set
FDA	Food and Drug Administration (United States)
FFPE	formalin fixed -paraffin-embedded
FIH	first in human
FISH	fluorescence in situ hybridization
FSH	follicle stimulating hormone
G-CSF	granulocyte-colony stimulating factor
GCP	Good Clinical Practice
GGT	gamma glutamyl transferase
GH	growth hormone
GI	gastrointestinal
GLP	Good Laboratory Practice
HBc	hepatitis B core
HBcAb	hepatitis B core antibody
HBsAb	hepatitis B surface antibody
HBsAg	hepatitis B surface antigen
HBV	hepatitis B virus
HCV	hepatitis C virus
HER2-	human epidermal growth factor receptor 2 negative
HER+	human epidermal growth factor receptor positive
HIV	human immunodeficiency virus
HLA-DR	human leukocyte antigen-antigen D related
HNSTD	highest non-severely toxic dose
HR	heart rate
HR+	hormone receptor positive

Abbreviation	Term
HRT	hormone replacement therapy
IB	investigator's brochure
ICANS	Immune Effector Cell-Associated Neurotoxicity Syndrome
ICD	informed consent document
ICE	immune effector cell-associated encephalopathy
ICH	International Council for Harmonisation
ICP	intracranial pressure
ICU	intensive care unit
ID	identification
IFN- γ	interferon-gamma
IGF-1	insulin-like growth factor 1
IgG	immunoglobulin G
IgG2	immunoglobulin G2
IgM	immunoglobulin M
IHC	immunohistochemistry
IL	interleukin
IMP	investigational medicinal product
IND	investigational new drug
INR	international normalized ratio
IP manual	investigational product manual
IPAL	Investigational Product Accountability Log
ir	immune-related
irAE	immune-related adverse events
IRB	institutional review board
irCR	immune-related complete response
irPD	immune-related progressive disease
irPR	immune-related partial response
IRR	infusion related reaction
irRECIST	immune related response criteria derived from RECIST 1.1
irSD	immune-related stable disease
IRT	interactive response technology
ISH	in situ hybridization
ISR	injection site reaction
IV	intravenous
IWR	interactive Web-based response
K2EDTA	dipotassium ethylenediaminetetraacetic acid
LBBB	left bundle branch block
LDH	lactate dehydrogenase
LDT	Laboratory Developed Test
LFT	liver function test
LH	luteinizing hormone
mAb	monoclonal antibody

Abbreviation	Term
MABEL	minimum anticipated biological effect level
MAP	meta-analytic-predictive
MD	multiple dose
MedDRA	Medical Dictionary for Regulatory Activities
MFI	mean fluorescence intensity
MHC	Major Histocompatibility Complex
ITT	modified intent to treat
MoA	mechanism of action
MRI	magnetic resonance imaging
MTD	maximum tolerated dose
mTNBC	metastatic triple negative BrCa
N/A	not applicable
NAb	neutralizing antibodies
NCI	National Cancer Institute
NIMP	non-investigational medicinal product
NK	natural killer cells
NOAEL	no-observed-adverse-effect level
NSAIDs	non-steroidal anti-inflammatory drugs
OR	objective response
ORR	objective response rate
OS	overall survival
OvCa	ovarian cancer
PaCO ₂	partial pressure of carbon dioxide
PBMC	peripheral blood mononuclear cell
PCR	polymerase chain reaction
PD	pharmacodynamics(s)/progressive disease
PD-1	programmed death-1
PD-L1	programmed death-Ligand 1
PE	physical examination
PET	positron emission tomography
PFS	progression-free survival
PI	principal investigator
PK	pharmacokinetic(s)
PR	partial response/progesterone receptor/ pulse rate
PRL	prolactin
PS	performance status
PT	prothrombin time
PTT	partial thromboplastin time
PVC	premature ventricular contraction/complex
Q1W	every 1 week
Q2W	every 2 weeks
Q3W	every 3 weeks

Abbreviation	Term
Q4W	every 4 weeks
QTc	corrected QT
QTcB	corrected QT (Bazett method)
QTcF	corrected QT (Fridericia method)
QTL	quality tolerance limit
R _{ac}	accumulation ratio
RDE	recommended dose for expansion
RECIST	Response Evaluation Criteria in Solid Tumors
RNA	ribonucleic acid
RP2D	recommended phase 2 dose
RR	respiratory rate
SAE	serious adverse event
SAP	statistical analysis plan
SARS-CoV2	severe acute respiratory syndrome coronavirus 2
SAS	safety analysis set
SC	subcutaneous
SD	single dose/stable disease/standard deviation
SISH	silver enhanced in situ hybridization
SOA	schedule of activities
SOC	standard of care
SOP	standard operating procedure
SRSD	single reference safety document
ss	steady state
SUSAR	suspected unexpected serious adverse reaction
T	T cell
t _½	terminal elimination half-life
T4	thyroxine
TBili	total bilirubin
TCR	T cell receptor
TIL	tumor infiltrating lymphocytes
T _{max}	time to maximum concentration
T _{max,ss}	time to maximum concentration at steady state
TME	tumor microenvironment
TNBC	triple negative BrCa
TNF	tumor necrosis factor
TSH	thyroid-stimulating hormone
TTP	time to progression
ULN	upper limit of normal
US	United States
V _{ss}	volume at steady-state
VAAST	Vasopressin and Septic Shock Trial
CCI	

Abbreviation	Term
V _z /F	apparent volume of distribution during terminal phase
WBC	white blood cell
WNL	within normal limits
WOCBP	woman/women of childbearing potential

